9.1 Adverse Events

9.1.1 Definition of Adverse Event

An AE is any untoward medical occurrence in a participant administered a pharmaceutical product, regardless of causal relationship with this treatment. An AE can therefore be any unfavorable and unintended sign (including an abnormal laboratory finding), symptom, or disease temporally associated with the use of a medicinal product, whether considered related to the medicinal product or not. For surgical or diagnostic procedures, the condition/illness leading to such a procedure is considered as the AE rather than the procedure itself. All AEs observed by the study personnel or reported by the participant during the study (from the time of signing the Informed Consent Form (ICF) to Visit 12 will be documented. Investigators must assess the severity of AEs according to the Qualitative Toxicity Scale, as follows:

Version Version 3.0_07FEB2023

Mild: The participant is aware of the event or symptom, but the event or symptom is easily

tolerated.

Moderate: The participant experiences sufficient discomfort to interfere with or reduce his or her

usual level of activity.

Severe: Significant impairment of functioning: the participant is unable to carry out his or her

usual activities.

Investigators must also systematically assess and reevaluate based on emergence of information, the causal relationship of AEs to IMP as Unrelated or Related. Decisive factors for the assessment of causal relationship of an AE to IMP include, but may not be limited to, temporal relationship between the AE and the IMP administration, known side effects and mode of action of IMP, medical history and comorbidity of the participant, concomitant medication, course of the underlying disease and trial procedures.

Unrelated: Not reasonably related to the IMP. AE could not medically

(pharmacologically/clinically) be attributed to the IMP under study in this clinical trial

protocol. A reasonable alternative explanation must be available.

Related: Reasonably related to the IMP. AE could medically (pharmacologically/clinically) be

attributed to the IMP under study in this clinical trial protocol.

9.1.2 Abnormal Laboratory Findings and Other Abnormal Investigational Findings

Safety parameters (including vitals, ECG, body weight and laboratory tests) with absolute value outside the reference range or changed following Screening that are considered by the Investigator as clinically significant must be recorded in the eCRF as AEs. In addition, at the Investigator's discretion, any changes, or trends over time in laboratory parameters can be recorded in the eCRF as AEs if such changes or trends are clinically relevant, even if the absolute values are within the reference range.

Laboratory findings do not need to be reported as AEs in the following cases:

- Laboratory parameters already outside the reference range at Visit 1, unless a further increase/decrease can be considered an exacerbation of a pre-existing condition.
- Abnormal laboratory parameters caused by mechanical or physical influences on the blood sample (e.g., hemolysis) and flagged as such by the laboratory in the laboratory report.

An abnormal laboratory value that cannot be confirmed and after a repeated analysis is considered within normal range should not necessarily be reported as an AE. A repeated analysis should preferably (but not required) to be completed in the same laboratory.

If a laboratory abnormality fulfills these criteria, the identified medical condition (for example, anemia, increased liver parameters) must be reported as the AE rather than the abnormal value itself.

Version

Version 3.0_07FEB2023

Clinically significant abnormal laboratory values, relevant findings from physical examination, ECG findings, radiograph- and MRI findings from Screening are considered likely to have been present at time of signing of ICF and regarded as Medical History, unless a significant exacerbation of the condition is plausible to have occurred between the time of ICF signature and time of abnormal finding.

9.1.3 Serious Adverse Events

An SAE is any untoward medical occurrence that at any dose:

- Results in death.
- Is life-threatening. (Note: The term "life-threatening" refers to an event in which the participant is at risk of death at the time of the event, not an event that hypothetically might have caused death if it was more severe.)
- Requires inpatient hospitalization or prolongs an existing hospitalization.
- Results in persistent or significant disability or incapacity
- Is a congenital anomaly or birth defect.
- Is otherwise considered to be medically important. (Note: Important medical events that may not result in death, be life-threatening, or require hospitalization may be considered as SAEs when, based upon appropriate medical judgment, they may jeopardize the participant or may require medical or surgical intervention to prevent one of the outcomes listed above. Examples of such events include allergic bronchospasm requiring intensive treatment in an emergency room or at home, blood dyscrasias or convulsions that do not result in inpatient hospitalization, or the development of drug dependency or drug abuse.)

For the purposes of reporting, any suspected transmission of an infectious agent via an IMP is also considered an SAE.

9.1.4 Events that Do Not Meet the Definition of an SAE

Elective hospitalizations to administer, or to simplify trial treatment or trial procedures are not considered SAEs. However, all events leading to unplanned hospitalizations or unplanned prolongation of an elective hospitalization (for example, undesirable effects of any administered treatment) must be documented and reported as SAEs.

9.1.5 Events Not to Be Considered as AEs/SAEs

Medical conditions present at the initial trial visit that do not worsen in severity or frequency during the trial are defined as Baseline Medical History and are not to be considered AEs.

Version Version 3.0_07FEB2023

9.1.6 Methods of Recording and Assessing Adverse Events

At each trial visit, the participant will be asked about changes in his or her condition. During the reporting period, any unfavorable changes in the participants condition will be recorded as AEs, whether reported by the participant or observed by the investigator.

Complete, accurate and consistent data on all AEs experienced for the duration of the reporting period (defined below) will be reported on an ongoing basis in the appropriate section of the eCRF. All SAEs and all nonserious AEs of special interest must be additionally documented and reported accordingly.

It is important that each AE report include a description of the event, its duration (onset and resolution dates (and times when it is important to assess the time of AE onset relative to the recorded treatment administration time), its severity, its causal relationship with the trial treatment, any other potential causal factors, any treatment given or other action taken, including dose modification or discontinuation of the IMP, and its outcome. In addition, serious cases should be identified, and the appropriate seriousness criteria documented.

9.1.7 Definition of the Adverse Event Reporting Period

The AE reporting period for safety surveillance begins when the participant is initially included in the trial (date of signature of ICF) and continues until Visit 12 (Follow-up Safety Phone Visit).

Any SAE assessed as related to LEVI-04 must be reported whenever it occurs, irrespective of the time elapsed since the last administration of LEVI-04.

9.1.8 Definition of SAE Reporting Period

In the event of any new SAE occurring during the reporting period, the Investigator must immediately (within a maximum of 24 hours after becoming aware of the event) inform the Sponsor or its designee in writing. All written reports should be transmitted using the SAE Report Form, which must be completed by the Investigator following specific completion instructions.

Relevant pages from the eCRF may be provided in parallel (for example, medical history, concomitant drugs). Additional documents may be provided by the Investigator, if available (for example, laboratory results, hospital report, autopsy report). In all cases, the information provided on the SAE Report Form must be consistent with the data about the event recorded in the eCRF.

The Investigator must respond to any request for follow-up information (for example, additional information, outcome, final evaluation, other records where needed) or to any question the Sponsor/designee may have on the AE within the same timelines as those noted above for initial reports. This is necessary to ensure prompt assessment of the event by the Sponsor or designee and (as applicable) to allow the Sponsor to meet strict regulatory timelines associated with expedited safety reporting obligations. An internal Safety Monitoring Committee (SMC) will review SAEs and other relevant safety data as needed as further described in the Safety Monitoring Committee Charter.

Version Version 3.0 07FEB2023

9.1.9 Adverse Events of Special Interest (AESI)

Owing to the action of LEVI-04 on NGF, neurological AEs are of special interest. The following are considered AESIs:

- AE suggestive of new or worsening peripheral neuropathy
- AE of abnormal peripheral sensation (e.g. allodynia, burning sensation, carpal tunnel syndrome, dysesthesia, hyperesthesia, hyperpathia, hypoesthesia, neuralgia, neuritis, neuropathy peripheral, pall anesthesia, paresthesia, peripheral sensory neuropathy, sciatica, sensory disturbance, sensory loss, or tarsal tunnel syndrome) that is reported as an:
 - o SAE
 - o AE that resulted in the participant being withdrawn from the study.
 - o AE ongoing at the end of study participation in the study or,
 - o AE of severe intensity.
- Destructive Arthropathy, including RPOA type 2
- SIF
- Rapid loss of joint space width (JSW) of 2 mm within 12 months or less, or loss of 50% of JSW if less than 2 mm at baseline. This is also known as RPOA type 1
- Osteonecrosis
- Any incident acute fracture or bone marrow infiltration.
- Total and partial joint replacement

Suspected events will be monitored by the Safety Monitoring Committee, and any events involving joint safety will be escalated to the Independent Adjudication Committee for Adverse Events relating to Joint Safety, for committee review and appropriate recommendations for the individual participant, and potentially the study. The Adjudication Committee for Adverse Events relating to Joint Safety includes at least one rheumatologist and at least one radiologist who are experts in this field as well as the coordinating Investigator and study Medical Monitor or delegates as further described in the Adjudication Committee for Adverse Events relating to Joint Safety Charter.

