3.2 Scientific Rationale and Role of Target in the Disease

LEVI-04's primary mode of action is inhibition of the activity of the Neurotrophins; Nerve Growth Factor (NGF) and Neurotrophin-3 (NT3) to reduce pain.

NGF is an important mediator of pain associated with OA⁹. Monoclonal antibodies against NGF showed efficacy in treating chronic pain due to OA in phase III clinical trials^{10,11}. However, risk of Rapidly Progressing Osteoarthritis (RPOA)¹² and adverse effects on the sympathetic nervous system¹³ raised concerns regarding their safety.

LEVI-04 is a fusion protein and thus has a different antagonist profile to anti-NGF antibodies and differs on several points:

Version

Version 3.0 07FEB2023

- Unlike anti-NGF antibodies that require plasma concentrations ~1000-fold the primary affinity to demonstrate efficacy in clinical studies¹⁰, LEVI-04 is efficacious in preclinical models of OA at concentrations of its potency for inhibition of NGF activity.
- LEVI-04 exhibits a more gradual inhibition of NGF-induced activity compared with anti-NGF antibody mediated inhibition.
- Multiple preclinical studies, including comparative histopathology and neuropathological
 evaluation studies of LEVI-04 and anti-NGF antibodies, have been performed specifically to
 address any safety concerns (See IB for full overview). These studies confirmed the detrimental
 effects of anti-NGF antibodies, but found no evidence of such effects of LEVI-04 at therapeutic
 doses.

Together, this indicates LEVI-04 to not be associated with the known risk of RPOA associated with anti-NGF antibodies. Conversely, treatment with LEVI-04 was found to be associated with improvements in the histopathological assessments compared to the control animals, which could indicate a beneficial disease-modifying effect of LEVI-04. These preclinical findings support the investigation of LEVI-04 as a novel drug for the treatment of OA.

For a full description of the modalities of LEVI-04 and study references, see Description of the Investigational Medical Product (Section 6.1.1) and Investigators Brochure (IB).

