4.16.2 Adverse Events

An AE is defined as "any untoward medical occurrence in a participant administered a pharmaceutical product, regardless of causal relationship with this treatment". An AE can therefore be any unfavorable and unintended sign (including an abnormal laboratory finding), symptom, or disease temporally associated with the use of a medicinal product, whether considered related to the medicinal product or not. For surgical or diagnostic procedures, the condition/illness leading to such a procedure is considered as the AE rather than the procedure itself.

An event will be considered a treatment-emergent AE (TEAE) if the start or worsening of the event was on or after the administration of IP. Summaries of adverse events will be limited to TEAEs, but listings of all events will be provided. A serious adverse event is an event recorded as 'Serious' on the adverse event eCRF page. Adverse events will be classified by MedDRA SOC and PT.

The overall summary of TEAEs will include frequencies and percentages and will be presented for the following:

- Overview of adverse events;
- All adverse events by SOC and PT;
- Serious adverse events by SOC and PT;
- Adverse events of special interest by SOC and PT;
- Adverse events by SOC, PT, and severity;
- Adverse events related to study treatment by SOC and PT

Relationship to study drug will be classified as "unrelated" or "related". The severity of an adverse event will be rated by the investigator as "mild", "moderate", or "severe". Participants experiencing multiple instances of the same PT are only counted once within each SOC and PT combination. Participants experiencing multiple instances of the same PT will only be counted

LEVI-04-21-02 Statistical Analysis Plan	Version: Final 3.0
Date: 18-Mar-2024	Page 27 of 34

once according to the highest severity during the treatment emergent period when summarizing severity.

Serious adverse events, if present, also will be listed using verbatim, SOC, and PT. Should any serious adverse events occur during the study, the serious adverse events are displayed in a table and a narrative for each serious adverse event included in the study report.

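### The AESI list omits autonomic and sympathetic events although the protocol names that concern, so non-serious cases miss AESI reporting and have no prespecified AE grouping

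*Protocol*

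**What the plan says.** Protocol 3.2, repeated in the SAP introduction, gives two reasons for concern about anti-NGF antibodies: rapidly progressive OA (RPOA) and "adverse effects on the sympathetic nervous system".

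Protocol 9.1.9 opens its AESI section with "Owing to the action of LEVI-04 on NGF, neurological AEs are of special interest" and then lists what counts as an AESI. The list has two neurological items. The first is "AE suggestive of new or worsening peripheral neuropathy", with no further condition. The second is "AE of abnormal peripheral sensation", illustrated with peripheral sensory and nerve terms. It counts only if the event is serious, leads to withdrawal, is ongoing at the end of participation, or is severe. The other items are joint and bone events, including RPOA types 1 and 2, and joint replacement.

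AESI status has consequences. Protocol 9.1.6 states: "All SAEs and all nonserious AEs of special interest must be additionally documented and reported accordingly". Protocol 9.1.9 assigns suspected listed events to the Safety Monitoring Committee. SAP 4.16.2 plans a table of "Adverse events of special interest by SOC and PT".

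Both documents also list a safety endpoint of peripheral nervous system AEs by count and severity (Protocol Table 2, SAP Table 1). Neither says which terms it contains.

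**The concern.** Of the two concerns in Protocol 3.2, RPOA is carried into the AESI list and the sympathetic one is not. The omission is hard to read as a decision that the risk is irrelevant to LEVI-04. Section 9.1.9 ties its neurological AESIs to the drug's own action on NGF. The trial also excludes people with an SAS symptom count above 3 and repeats the SAS on study.

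What is at stake is whether autonomic AEs can be read by dose. Protocol 5.2 says the trial is meant to add to the safety data and to establish the most suitable Phase 3 dose. The general AE tables are split by system organ class and preferred term, so related events reported under different terms are counted in separate rows. Without a group fixed in advance, any later grouping would be chosen with the treatment results known.

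**Working it through.** The plan states no figure on this point, so the check is mainly a comparison of sections.

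**1. What a non-serious autonomic AE triggers by rule**

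| Provision | Applies to a non-serious autonomic AE? |
|---|---|
| AE recording with severity, causality and outcome (Protocol 9.1.1, 9.1.6) | Yes |
| Additional AESI documentation and reporting (Protocol 9.1.6) | No, unless reported as peripheral neuropathy |
| Committee monitoring tied to the AESI list (Protocol 9.1.9) | No, with the same exception |
| AESI table (SAP 4.16.2) | No, with the same exception |
| General tables by organ class and preferred term (SAP 4.16.2) | Yes, if treatment-emergent, but ungrouped |
| Peripheral nervous system AE endpoint | Unknown: no term list, and no table of that name in SAP 4.16.2 |

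**2. Whether the SAS fills the gap**

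Inputs: recall of six months (Protocol 7.9.3, SAP 4.9); on-study surveys at Day 57 ±3 and Day 141 ±3 (Protocol Table 1); first dose on Day 1. Assumption: six months is about 182 days.

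Pre-treatment part of the window = recall length − (survey day − 1).

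- Day 57: 182 − 56 = 126 days before first dose, or 126/182 = 69% of the window.
- Day 141: 182 − 140 = 42 days before first dose, or 42/182 = 23% of the window.

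With six months taken as 180 to 184 days and the visit windows used in full, the ranges are 121 to 131 days (180 − 59; 184 − 53) and 37 to 47 days (180 − 143; 184 − 137). Both windows include pre-treatment time throughout. A 'yes' at either survey may therefore refer to a symptom from before the first dose, and the form as described does not date onset.

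The SAS exclusion is a count above 3, so a participant may enter with 3 symptoms. SAP 4.9 and 4.14 summarise counts only up to three or more. A participant going from 3 to 6 symptoms stays in the same category, and only the change in total impact score could show it. The last SAS is at Week 20, while AE collection runs to Visit 12 at Week 30 (Protocol 9.1.7).

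**3. Whether vital signs fill the gap**

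Vital signs are taken sitting or lying (Protocol 7.5), and no standing reading is stated. Protocol 10.4.7 says thresholds for potentially clinically significant values will be defined in the SAP; SAP 4.16.3 gives none.

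**The case against.** The strongest reply is that autonomic safety is watched by other routes, and much of that stands.

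- Protocol 9 has the Safety Monitoring Committee evaluate safety periodically, with no restriction to AESIs. Protocol 9.1.8 adds review of SAEs and other relevant data as needed.
- Significant vital-sign changes are reviewed centrally and brought to the sponsor when necessary (Protocol 9.7). Clinically significant vital-sign and ECG findings are recorded as AEs (Protocol 9.1.2).
- AEs that are the primary reason for withdrawal are documented, reported and followed (Protocol 5.4.1).
- SAP 4.14 summarises SAS symptom counts and impact score by gender, treatment and visit. The two recall windows together cover Day 1 to Week 20 without a gap.
- The unconditional neuropathy item could capture an event reported as autonomic neuropathy.
- Protocol 3.2 states the sympathetic concern for antibodies and argues that LEVI-04 differs. The Phase 1 SAS results in healthy volunteers showed no dose-related effect.

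A reader might infer from the AESI list that non-serious autonomic events are never escalated, or are not monitored at event level. The documents do not support that: the routes above exist, and the committee charter, medical monitoring plan and pharmacovigilance plan are not among the documents, so absence of escalation cannot be shown.

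The reply does not remove the narrower point. Committee review beyond SAEs is as needed and, in these documents, defines no autonomic category. The SAS is questionnaire data with the limits shown above. The antibody argument sits uneasily with the reason 9.1.9 gives for its own list.

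**Conclusion.** The point holds in a limited form. The AESI list omits a category that Protocol 3.2 names as a concern. Non-serious autonomic or sympathetic AEs consequently fall outside AESI reporting, AESI-linked committee monitoring and the AESI table, and no AE grouping is prespecified for them. The other safeguards compensate in part.

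The consequence is moderate: it affects how readable the descriptive safety data are by dose, not the primary analysis. Protocol 10.4.7 plans no inference on safety endpoints, so a grouped row would improve visibility and would not provide a significance test. No number of affected events can be given without inventing rates. The finding assumes that 9.1.9 means its list to be exhaustive, as its lead-in suggests. The SAS argument assumes six months is about 182 days, and its direction does not depend on the exact value.

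**What to change.** 1. In SAP 4.16.2, add one grouped row for treatment-emergent AEs suggestive of autonomic or sympathetic dysfunction, by arm and at any severity. The sponsor should choose the preferred-term list and fix it before unblinding. A separate row is needed because the planned AESI table is itself split by organ class and preferred term.
2. State in the SAP which terms make up the peripheral nervous system AE endpoint, and whether the autonomic terms are among them.
3. Reconcile Protocol 9.1.9 with 3.2 by adding the category to the AESI list, if reporting can still be changed. If it cannot, item 1 still works on AEs already collected.

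The cost is a term list, one table row and, under item 3, some protocol wording and a modest number of extra AESI reports. It adds no procedure or visit and does not alter patient care.

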	 AEs between treatment arms (Count and Severity) Peripheral Nervous System AEs between treatment arms (Count and Severity) Incidences of Joint Events and subtypes of Joint Events. Events include: Osteonecrosis Destructive Arthropathy, including RPOA type 2 Changes in signs of inflammation on MRI of the Target Knee, Subchondral insufficiency fracture Rapid loss of joint space width (JSW) by 2 mm within 12 months or loss of 50% of JSW if less than 2 mm at baseline. This is also called RPOA type 1 Any other incidence of joint events such as acute fracture, bone marrow infiltration, etc. 					
	Incidence of surgical interventions including joint replacement.					
Statistical Methods	An interim analysis (IA) will be performed for sample size re-estimation when approximately 208 participants have completed study Visit 6 (week 5) and approximately 80 patients have completed Visit 10 (week 17).					

CONFIDENTIAL Clinical Trial Protocol

LEVI-04-21-02

Version Version 3.0_07FEB2023

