To explore associations of biomarkers of the neurotrophin signaling pathway and pain severity	Change from baseline in blood biomarkers and associations with clinical outcomes

LEVI-04-21-02 Statistical Analysis Plan	Version: Final 3.0
Date: 18-Mar-2024	Page 12 of 34

Objective(s)	Endpoint(s)	
Safety		
To evaluate the overall safety of LEVI-04 compared to placebo.	Adverse Events (AEs) between treatment arms (Count and Severity)	
To evaluate the safety of LEVI-04 compared to placebo in relation to the peripheral nervous system.	Peripheral Nervous System AEs between treatment arms (Count and Severity)	
To evaluate the safety of LEVI-04 compared to placebo in relation to joint safety.	Incidences of Joint Events and subtypes of Joint Events. Events include: Osteonecrosis Destructive Arthropathy, including Rapidly Progressive Osteoarthritis (RPOA) type 2 Changes in signs of inflammation on MRI of the Target Knee, Subchondral insufficiency fracture Rapid loss of joint space width (JSW) by 2 mm within 12 months or loss of 50% of JSW if less than 2 mm at baseline. This is also called RPOA type 1. Any other incidence of joint events such as acute fracture, bone marrow infiltration, etc.	

LEVI-04-21-02 Statistical Analysis Plan	Version: Final 3.0
Date: 18-Mar-2024	Page 13 of 34

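### Joint replacement is an AESI and a synopsis safety endpoint, but the AE rules can file it under the underlying condition, and the SAP plans no incidence by arm

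*Protocol*

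**What the plan says.** Two places in the protocol treat joint replacement as an outcome in its own right. Section 9.1.9 lists "Total and partial joint replacement" as an AESI. The safety endpoints in the synopsis include "Incidence of surgical interventions including joint replacement".

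The recording rules point the other way. SAP 4.16.2, repeating Protocol 9.1.1, states: "For surgical or diagnostic procedures, the condition/illness leading to such a procedure is considered as the AE rather than the procedure itself". Protocol 9.1.5 adds a second filter: "Medical conditions present at the initial trial visit that do not worsen in severity or frequency during the trial are defined as Baseline Medical History". Such conditions are not AEs. Neither section mentions the AESI list.

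On reporting, SAP 4.16.2 plans one AESI display, "Adverse events of special interest by SOC and PT", among summaries limited to treatment-emergent events. SAP 4.16.7 summarizes minimum joint space width (mJSW) and rapidly progressive osteoarthritis (RPOA) from X-ray. The joint-safety rows of Protocol Table 2 and SAP Table 1 do not mention surgery. The nearest item is the open category "Any other incidence of joint events such as acute fracture, bone marrow infiltration, etc". SAP section 6, which lists departures from the protocol, is silent on the surgery endpoint.

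**The concern.** Joint safety is a stated objective of the trial, and the protocol chose joint replacement as one of the ways to judge it. A site that follows the general AE rule would enter the condition that led to the operation. In this population that condition will often be osteoarthritis, which every participant has at baseline. A replacement entered that way cannot be told apart, in a table by preferred term, from worsening of the same condition without surgery. If sites read the rule differently, some replacements will carry a procedure term and others a condition term.

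At stake is whether the report can state how many participants in each arm had a joint replaced. As written, the plan specifies no display that answers this, although the synopsis says the incidence is an endpoint.

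**Working it through.** No figure in the plan is in dispute, so the check is to follow a replacement through the rules and see where it would appear.

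**Step 1. How it is recorded.** There are three cases.
- *The condition has worsened since baseline.* Under Protocol 9.1.1 the AE is the condition. The replacement is at most an action taken, which Protocol 9.1.6 asks to be described in the AE report.
- *The condition has not worsened.* Under Protocol 9.1.5 it stays baseline medical history, so there may be no AE record to carry the replacement.
- *The site treats 9.1.9 as overriding 9.1.1.* The event is flagged as an AESI. The text still does not say which term to enter, and SAP 4.16.2 repeats the condition rule without exception.

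**Step 2. Where it is tabulated.** In the first case it falls under the condition's preferred term. In the third case the AESI table is also by preferred term, so it isolates replacements only if sites entered a procedure term, contrary to the general rule. In the second case it reaches no AE table. SAP 4.16.7 does not help, because it covers mJSW and RPOA. The broader wording at the start of SAP 4.16 extends the imaging measures, not surgery.

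**Step 3. Whether the endpoint is assigned an analysis elsewhere.** It appears in the synopsis but not in Protocol Table 2 or SAP Table 1. The open category in those tables could be stretched to include a replacement, but the SAP attaches no display to it. SAP section 6 does record that the imaging-biomarker analyses are postponed, so it is the place where a dropped analysis would be expected. The surgery endpoint is not there.

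**Step 4. What the other routes deliver.**
- SAE table, verbatim listing and narrative (SAP 4.16.2): these would cover a replacement reported as an SAE because of an inpatient stay, but the term is still the condition's.
- Additional AESI documentation (Protocol 9.1.6): this applies to AEs of special interest, so it presupposes an AE.
- Adjudication (Protocol 9.1.9): joint-safety events are escalated, but the SAP plans no table of adjudicated replacements by arm.
- Radiographs (Protocol 7.12): knees, hips and shoulders are imaged at Week 20, replaced joints included. Follow-up runs to Week 30, so the last 30 − 20 = 10 weeks have only the Visit 12 telephone review of AEs and concomitant medication.
- Listings (SAP 4.1): these show what was collected, by participant, not as an incidence.

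Each route may reveal a replacement. None is planned to produce a count by arm.

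**Scale of one event.** With 416/4 = 104 per arm, one participant is 1/104 = 0.96 percentage points of the arm's incidence. With 624/4 = 156 it is 1/156 = 0.64 points. This shows what one unidentified replacement does to a descriptive percentage. It is not a forecast of how many there will be.

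**The case against.** The strongest reply is that a replacement is hard to lose. One needing an inpatient stay would normally meet the SAE definition and so receive a verbatim listing and a narrative. AESIs get additional documentation, joint events go to adjudication, and Week 20 films would show a new prosthesis in a knee, hip or shoulder. Exclusion criterion 8 bars participants with planned major surgery, and Protocol 9.1.6 asks for any unfavorable change to be recorded. Surgery for a wholly unchanged condition, with no AE at all, should therefore be uncommon. A specific AESI entry can also be read as overriding a general convention. Finally, the eCRF completion guideline and the adjudication charter are not among the documents, and either might already provide a form for replacements.

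Most of this stands, and it limits the point. A reader might infer that replacements would go uncounted altogether, or that the AE rule suppresses them. The documents do not support that: the rule is a general convention and there are several routes by which a replacement could come to light. A reader might also be tempted to quote an upper confidence limit for zero observed replacements. Protocol 10.4.7 plans no inference on safety endpoints, so such a limit would describe an analysis that the trial does not intend.

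What the reply does not supply is the missing analysis. Narratives, adjudication records, films and listings are not an incidence by arm, and the films stop at Week 20. Reading 9.1.9 as an exception is reasonable, but no text says so, and SAP 4.16.2 restates the opposite rule.

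**Conclusion.** The point holds as an inconsistency with a consequence for reporting. The AESI list and the AE rules conflict on how a joint replacement is recorded. As written, a replacement can be filed under the underlying condition's term, and a safety endpoint named in the synopsis has no planned incidence by arm and no recorded reason for its absence. Counts may therefore be incomplete or hidden under another term. It does not follow that they will be.

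The extent is one endpoint and one AESI. The documents give no replacement rate, so the number of events affected cannot be estimated. The conclusion assumes that sites follow the AE rule as written and that no form outside these documents feeds an unlisted table. It should be corrected before the safety tables are finalized, but it does not touch the primary analysis.

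**What to change.** 1. Reconcile Protocol 9.1.1 and 9.1.5 with 9.1.9 so that each joint replacement is identifiable as an AESI whatever AE term is coded, including when the underlying condition has not worsened.
2. Name the data source in the SAP: the existing AESI or adjudication form if it captures joint, date and reason, or a procedure field if no such form exists.
3. Restore the surgical-intervention endpoint to Protocol Table 2 and SAP Table 1.
4. Add to SAP 4.16 a descriptive table of participants with joint replacement or other joint surgery, by arm and joint, from first dose to Visit 12, on the Safety Analysis Set.

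If the sponsor has instead decided to drop the endpoint, SAP section 6 should say so and give the reason.

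The cost is a reconciling sentence in the protocol, one row in each endpoint table and one SAP table. A data-collection change is needed only if no current form records replacements. No visit or procedure is added.
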